1. SYNOPSIS

Study Title	SeveriTy of Pulmonary Edema and timing of Resolution in patients with severe pre-eclampsia and eclampsia (TIPER) – a prospective observational study		
Internal ref. no. (short title)	Pulmonary edema resolution in severe pre-eclampsia and eclampsia – TIPER		
Study Design	A prospective, observational cohort st	udy.	
Study Participants	Female subjects, hospitalized with seven	ere preeclampsia or eclampsia	
Planned Sample Size	All eligible patients admitted to PCMH for 1 year		
Study Site	Princess Christian Maternity Hospital,	Freetown, Sierra Leone	
Planned Study Period	April 2023 to April 2024.		
Inclusion criteria	All patients with severe pre-eclampsia during the study period	or eclampsia admitted to hospital PCMH	
Exclusion criteria	 Patients with chronic hypertensive disorders Lung ultrasound not feasible, e.g., due to electricity breakdown, or absence of the trained sonographer or presence of subcutaneous emphysema, 		
Aim	The primary aim is to describe the frequency of lung ultrasound consistent with pulmonary oedema and the timing of resolution after delivery. Secondary aims include the assessment of the frequency of acute respiratory		
	failure, other LUS findings beyond pulmonary edema, the assessment of oxygenation, the use of respiratory organ support strategies, assessment of cardiac function, and quantification of major direct/ indirect obstetric complications and of perinatal complications.		
Hypothesis	 A high proportion (>20%) of patients show LUS signs consistent with pulmonary edema before delivery. There is incomplete resolution of both clinical and ultrasound signs of pulmonary edema 48 hours after delivery. 		
	Objectives	Outcome Measures	
Primary	Frequency of LUS consistent with pulmonary edema	Frequency endpoint: proportion of patients with a LUS positive for pulmonary edema Severity: LUS areation score	
	Timing of resolution after delivery	Categorical: Fraction of patients with improvement or resolution of LUS findings. Numerical: delta LUS score between T1 and T2	
Secondary	Frequency of acute respiratory failure in patients with Severe Pre eclampsia and in patients with Eclampsia	Proportion of patients with acute respiratory failure	

	Frequency of other LUS findings	 Proportion of patients with consolidations isolated pleural effusion 	
		minor LUS findings	
	Frequency of organ support strategies	Fraction of patients that receive oxygen and/or CPAP and/or mechanical ventilation	

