4. OBJECTIVES AND OUTCOME MEASURES

Objectives	Outcome Measures	
Primary objective		
To describe the frequency of LUS abnormalities consistent with pulmonary oedema	Frequency endpoint: proportion of patients with LUS consistent with pulmonary edema Severity endpoint: LUS aeration score (numerical 0 to 36)	
To describe the timing and entity of edema resolution after delivery	Frequency endpoint: Fraction of patients with improvement or resolution of LUS findings. Quantitative endpoint: delta LUS score between T1 and T2	
Secondary objectives: To describe the frequency of acute respiratory failure in patients with Severe Pre- eclampsia and in patients with Eclampsia	Proportion of patients with acute respiratory failure (see definition)	
Frequency of other LUS findings	 Proportion of patients with: consolidations isolated pleural effusion minor LUS findings Calculation of the LUS ARDS score 	
Frequency of organ support strategies	Fraction of patients that receive: - oxygen - CPAP - Mechanical ventilation	
Frequency of patients with abnormal cardiac function	Defined as either low cardiac output measured by ultrasound	
Oxygenation assessment	SpO ₂ to FiO ₂ ratio	
Frequency of Major Direct Obstetric Complications	Fraction of patients with at least one additional MDOC (APH, PPH, sepsis, uterine rupture, obstructed labour)	
Frequency of Indirect Obstetric complications	Fraction of patients with at least one among stroke, severe malaria, acute kidney injury and cardiac insufficiency	
Frequency of perinatal complications	IUFD, Apgar score, Admission to special care baby unit (SCBU)	

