4.1 Hypothesis

- 1. A high proportion (>20%) of patients show LUS signs consistent with pulmonary edema before delivery.
- 2. There is a resolution of both clinical and ultrasound signs after in the 48 hours after delivery.

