5. STUDY DESIGN

This will be a single centre, prospective, cohort study of patients with severe pre-eclampsia and eclampsia. The expected duration of study is 1 year. All patients with suspected severe pre-eclampsia or eclampsia will undergo screening upon admission to HDU and the Eclamptic ward. Eligible patients will undergo a systematic clinical and LUS examination, straight after admission (**before delivery**). Clinical examination will focus on signs of respiratory, neurologic and cardiac failure. Lung ultrasound will be performed using a MyLab[™]Five ultrasound machine (Esaote Spa, Genova, Italy) and a low frequency (2.5–5 MHz) convex probe or a Butterfly ultrasound probe (Butterfly, USA). Lung ultrasound will be performed using the

validated 12-region method, evaluating 2 anterior regions, 2 lateral regions and 2 posterior in each hemithorax (18,28,29). As heart failure is a common finding in preeclamptic women, echocardiography performed with a cardiac sector probe, will enable real-time assessment of maternal cardiac contractility and cardiac output. The same clinical, LUS and echocardiographic assessment will be repeated between 24 h to 72 h (after delivery). Whenever the pre-delivery timepoint is not feasible due to late arrival, emergency scenario or postpartum onset, the after delivery examination only will be performed.

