10. STATISTICS AND ANALYSIS

For descriptive purposes continuous and ordinal variables data will be expressed as median with interquartile range. For categorical variables, percentages are calculated. Student's t-test or analysis of

variance (ANOVA) will be used to compare normally distributed numerical variables. Mann Whitney Utests and Kruskal-Wallis tests will be used to compare numerical variables when normality cannot be assumed, while chi-squared tests will be used to compare categorical variables. Univariate logistic regression analyses will be performed to identify potential factors associated with the clinical outcomes including, but not limited to, presence of interstitial syndrome, non-resolution of interstitial syndrome at 48-72h, development of ARDS and death in hospital. Multivariable logistic regression models will be used to identify independent risk factors for the same clinical outcomes. A forward and backwards stepwise approach will used to include variables into the models, with a limit of P <0.2.

Inter– observer variability of the lung ultrasound score between the study sonographer and an independent expert will be calculated on a random sample of 10 cases (120 lung regions) using Cohen K-statistics. Statistical analyses will be conducted using R (www.r-project.org). A P-value of <0.05 will be considered statistically significant. Analyses will be conducted after the end of patient recruitment and no interim analyses are planned. Statistical analysis will be performed with R software (R Foundation for Statistical Computing, Vienna, Austria).

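### The repeat scan is allowed at 24-72 h but non-resolution is modelled at 48-72 h; no rule covers scans before 48 h, and no planned analysis uses hours since delivery

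*Combined protocol and SAP*

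**What the plan says.** Section 5 (Study Design) places the first assessment before delivery. For the second it says: "The same clinical, LUS and echocardiographic assessment will be repeated between 24 h to 72 h (after delivery"). When the pre-delivery assessment is not feasible, "the after delivery examination only will be performed".

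Section 4 makes the timing and extent of resolution after delivery a primary objective. Its outcome measures are "Fraction of patients with improvement or resolution of LUS findings. Quantitative endpoint: delta LUS score between T1 and T2". Neither has hours attached, and no denominator is given.

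Section 10 plans univariate and stepwise multivariable logistic regression for several outcomes, one of which is "non-resolution of interstitial syndrome at 48-72h". It gives no time origin for those hours, names no candidate covariates and has no rule for scans taken before 48 h.

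Hypothesis 2 in the synopsis reads "There is incomplete resolution of both clinical and ultrasound signs of pulmonary edema 48 hours after delivery". In section 4.1 it reads "There is a resolution of both clinical and ultrasound signs after in the 48 hours after delivery".

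**The concern.** A woman scanned at 30 h and still positive has complied with the protocol, but her status at 48-72 h is unknown and no further scan is planned. The analyst must choose how to treat her, and the choice changes the estimated share unresolved and the risk-factor models built on it.

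The resolution fraction and the change in LUS score pool scans that may be up to 48 hours apart. With no analysis by hours since delivery, they say little about when oedema resolves, which is what the objective asks. If scan time is related to severity, which the documents do not address, the non-resolution models would also be confounded by it.

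Hypothesis 2 as it stands lets one result be described as supporting either version.

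**Working it through.** **Text comparison.** The plan states no figure on this point, so there is none to reproduce.

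| Place | Time stated |
|---|---|
| Section 5, repeat assessment | 24-72 h, after delivery |
| Section 10, modelled outcome | 48-72 h, origin not stated |
| Synopsis, hypothesis 2 | 48 h after delivery, resolution incomplete |
| Section 4.1, hypothesis 2 | within 48 h after delivery, resolution |
| Section 4, primary resolution endpoints | T1 to T2, no hours |

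Share of the permitted window before 48 h: (48 − 24)/(72 − 24) = 0.50.

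**Three ways to handle a scan at 24 to <48 h.**
1. Use only scans at 48-72 h. This is the literal reading of section 10. It is unbiased if scan timing is unrelated to resolution, but it discards compliant scans.
2. Label all scans 48-72 h. This overstates non-resolution whenever oedema clears over time.
3. Count early clear scans as resolved and set early positive scans to missing. This understates non-resolution.

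**Illustration of size, among women positive before delivery.** Input from the documents: section 3.1 cites a mean of 2.4 days to resolution, or 2.4 × 24 = 57.6 h. That figure covers mixed obstetric disorders, and the protocol states neither its clock start nor whether resolution was judged by ultrasound. Assumptions: the clock starts at delivery; resolution time is exponential, or lognormal with log-SD 0.3 to 1.0; scan times are uniform within each half of the window.

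Let E and L be the average probability of still being positive over 24-48 h and 48-72 h. For the exponential, S(t) = exp(−t/57.6) gives 0.659, 0.435 and 0.287 at 24, 48 and 72 h.

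| Shape | E | L | E − L |
|---|---|---|---|
| Exponential | 0.539 | 0.355 | 0.184 |
| Lognormal 0.3 | 0.891 | 0.403 | 0.489 |
| Lognormal 0.5 | 0.750 | 0.378 | 0.372 |
| Lognormal 0.8 | 0.581 | 0.331 | 0.250 |
| Lognormal 1.0 | 0.496 | 0.298 | 0.198 |

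Let w be the share of scans taken early. The documents give no distribution of scan times, so w is varied.
- Option 2 overstates the unresolved share by w(E − L).
- Option 3 gives (1 − w)L / [(1 − w) + w(1 − E)], to be compared with L.

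| w | Option 2, points too high | Option 3, points too low |
|---|---|---|
| 10% | 2-5 | 0.5-2 |
| 25% | 5-12 | 1-5 |
| 50% | 9-24 | 4-11 |
| 75% | 14-37 | 10-21 |

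Example for w = 50%, exponential. Option 2: 0.5 × 0.539 + 0.5 × 0.355 = 0.447 against 0.355, or 9 points too high. Option 3: 0.5 × 0.355/(0.5 + 0.5 × 0.461) = 0.243, or 11 points too low.

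**The case against.** The strongest reply is that the two windows are compatible: 48-72 h lies inside 24-72 h, so the analyst can simply use the scans taken then. That stands. A reader might infer that following the plan must yield an outcome that is either mislabelled or selectively missing. The documents do not support this, because the literal reading is neither. What remains is that the plan does not state this choice and does not say what becomes of the earlier scans.

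The time origin is also less certain than it looks. In section 5 the words on delivery could be labels for the two time points, and section 10 gives no origin. Hours since delivery is the natural reading, since both versions of hypothesis 2 count from delivery, but it is an inference.

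It can also be said that the study is exploratory and descriptive (section 5.1), that the outcome list is open ("potential factors associated with the clinical outcomes including, but not limited to"), and that scan time could be added later. The open wording concerns outcomes, not covariates. Stepwise selection at P <0.2 would not guarantee that scan time stays in a model. A descriptive estimate of timing still needs a time point and a denominator.

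T1 and T2 can be inferred from section 5 as the pre-delivery and post-delivery assessments, so the labels are not the defect.

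**Conclusion.** The point holds as an unreconciled conflict between the scan window and the modelled outcome window, with no rule for the early half. It should be fixed before analysis. The direction of error under each way of handling early scans needs only that oedema clears over time. The sizes are illustrative: they rest on the borrowed 2.4-day mean, the assumed shapes and an unknown share of early scans.

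Two stronger inferences should be resisted. First, the primary endpoints are not shown to be wrong by any stated amount. They carry no 48-72 h label, and the effect of pooling on them cannot be computed from the documents. The supportable statement is that, as planned, they say little about timing, and that women scanned only after delivery have no T1 and cannot contribute to either. Second, the opposed wordings of hypothesis 2 do not alter a test result, because no threshold or test is attached to it. The risk is one of interpretation. Confounding of the models by scan time is possible but is not established by anything in the documents.

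**What to change.** - Reconcile the synopsis, section 4.1, section 5 and section 10 to one stated time origin (hours since delivery), one outcome window and one direction for hypothesis 2.
- Record the times of delivery and of the T2 scan. Sections 7 and 8 name neither, though the case report form may already hold them.
- Report the fraction with improvement and the fraction with resolution separately, each among women whose pre-delivery scan was abnormal on the relevant measure. Report the change in LUS score among all women with paired scans. Give each overall and by 24 to <48 h and 48-72 h, with 95% CIs.
- Report clinical signs in the same strata, since hypothesis 2 covers them, and state the number of women scanned only after delivery.
- In the non-resolution models, either restrict to scans at 48-72 h, or use all T2 scans, name the outcome 24-72 h and force hours since delivery into the model. Do not label scans before 48 h as 48-72 h outcomes.

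The cost is wording, two time stamps if not already held, and at most one extra model term; no scans or patients are added. The downside is smaller strata. A stratum holding half the scans has a standard error 1/√0.5 = 1.41 times that of all scans. No target sample size is given, so stratum sizes are assumptions: at 35% unresolved, the Wilson 95% CI is 18-57% for 20 women, 22-50% for 40 and 25-46% for 80.

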5.1. Study Site

The study will be conducted at a single tertiary care hospital in Freetown, Sierra Leone. The Princess Christian Maternity Hospital (PCMH) is a 130-bed referral hospital. Patients will be recruited from the Eclamptic ward and the High Dependency Unit.

5.1. Sample size calculation

There is very limited data on the prevalence of pulmonary edema in eclampsia patients. For this explorative descriptive study we plan to recruit all eligible patients during a 12 months study period.

6. PARTICIPANT IDENTIFICATION AND RECRUITMENT

6.1. Study Participants

Patients hospitalized at PCMH with severe preclampsia and eclampsia will be enrolled if the applicable inclusion and exclusion criteria are met.

6.2. Inclusion Criteria

1. All patients with severe pre-eclampsia or eclampsia admitted to hospital PCMH during the study period, defined as by American College of Gynaecology and Obstetrics according to the Government of Sierra Leone Ministry of Health and Sanitation.

6.3. Exclusion Criteria

The participant may not enter the study if ANY of the following apply:

1. Patients with chronic hypertensive disorders;

2. LUS not feasible, e.g., due to electricity breakdown, or absence of the trained sonographer or diffuse subcutaneous emphysema.

6.4. Case definitions

Acute respiratory failure defined as RR≥30 breaths per minute AND/OR SpO₂/fraction of inspired oxygen (FiO₂) \leq 315 AND/OR signs of difficult breathing, including the use of accessory muscles or nasal flaring. FiO₂ will be derived from the amount of oxygen the patient receives in liters.

Clinical pulmonary oedema

Defined as respiratory distress (respiratory rate >30 breaths/min and/or SpO2 <92% on room air) with bilateral fine crepitations on chest auscultation.

Lung ultrasound consistent with pulmonary oedema (categorical)

The presence of three or more B-lines (any size and any distance apart) in a particular lung region will define a positive lung region for interstitial syndrome (30) Pulmonary edema will be defined as the presence of \geq 2 positive regions per side.

Abnormal lung ultrasound aeration score

The LUS aeration score (numerical) will be calculated: each lung field will be scored from 0 to 3 as follows: "0," A-pattern with \leq 2 B-lines; "1," more than 2 separated B-lines; "2," multiple coalescent B-lines; or "3," lung consolidation, defined as anechoic or tissue-like images arising from the pleural line that is limited in depth by an irregular border. A global LUS score will be calculated at each time point and ranged from 0 to 36.

LUS ARDS score

The three variables included in the final logistic regression model for diagnosis of ARDS are: left LUS aeration score (range 0-18), right LUS aeration score (range 0-18), and the number of antero-lateral lung regions with an abnormal pleural line (range 0-8). The LUS-ARDS score can range from 0 to 91 and is computed with the formula below. (31)

LUS-ARDS score = 2.5 x left LUS aeration score + 1 x right LUS aeration score + 3.5 x no. of anterolateral regions with an abnormal pleural line

Acute Respiratory Distress Syndrome (ARDS)

Defined according to the Berlin Definition or Kigali Modification as shown in **Table 1**.

Criteria	Berlin definition of ARDS	Kigali modification
Timing	Within 1 week of a known clinical insult, or new or worsening respiratory symptoms	
Oxygenation	PaO ₂ /FIO ₂ ≤300 mmHg SpO ₂ /FIO ₂ ≤315 mmHg	
PEEP requirement	Minimum 5 cm H ₂ O PEEP required by invasive mechanical ventilation (non-invasive acceptable for mild ARDS)	No PEEP requirement, consistent with AECC definition
Chest imaging	Bilateral opacities not fully explained by effusions, lobar/lung collapse, or nodules by chest radiograph or CT	Bilateral opacities not fully explained by effusions, lobar/lung collapse, or nodules by chest radiograph or ultrasound
Origin of oedema	Respiratory failure not fully explained by cardiac failure or fluid overload (need objective assessment, such as echocardiography, to exclude hydrostatic oedema if no risk factor present)	

Table 1. Berlin Criteria for ARDS and Kigali Modification of the Berlin Criteria (19,32)

Bilateral opacities on ultrasound will be defined as two or more regions with a B-pattern and/or C-patterns per hemithorax bilaterally (33).

Abbreviations: ARDS, acute respiratory distress syndrome; PaO2, arterial oxygen tension; FiO₂, fraction of inspired oxygen; SpO₂, oxygen saturation as measured by pulse oximetry; AECC, American-European Consensus Conference; CT, computed tomography; PEEP, positive end-expiratory pressure.

Abnormal cardiac function

Defined as a cardiac index (CI) <2.5 l/min/m2 measured by echocardiography.

Modified Early Warning (MEWS) Score

The modified early warning score ranges from 0 to 14 and is calculated as detailed in **Table 2** (34) (35).

Physiological parameters	Normal values (0 points)	Yellow alert (1 point)	Red Alert (2 points)
Respirator rate	10- 20 breaths pwe minute	21- 30 breaths per minute	<10 or >30 breaths per minutes
Oxygen saturation	96- 100%		<95%
Temperature	36.0- 37.4°C	35- 36 or 37.5- 38°C	<35 or >38°C
Systolic blood	100- 139 mmHg	150- 180 or 90- 100	>180 or < 90 mmHg
pressure		mmHg	
Diastolic blood	50- 89mmHg	90- 100 mmHg	>100 mmHg
pressure			
Heart rate	50- 99 beats per		>120 or <40 beats per minutes
	minute	100- 120 or 40- 50	
		beats per minute	
Neurological	Alert	Voice	Unresponsive, pain
response			

Table 2. The Modified Early Warning Score score.

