7.4.2. Physical exam and vital signs

Upon enrolment, a full physical examination will be conducted by a research physician. Vital signs including GCS, pulse rate, blood pressure, respiratory rate, SpO₂, FiO₂, aural temperature (average of left and right ears), weight, height and a neurological exam will be recorded in the CRF.

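### The SpO2/FiO2 item of acute respiratory failure is almost inert on room air and automatic from FiO2 of about 0.32, so some women with low room-air saturation are not counted

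*Combined protocol and SAP*

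**What the plan says.** Section 6.4 defines the outcome: "Acute respiratory failure defined as RR≥30 breaths per minute AND/OR SpO₂/fraction of inspired oxygen (FiO₂" at or below 315, or "signs of difficult breathing, including the use of accessory muscles or nasal flaring". The items are joined by AND/OR, so any one is enough. FiO2 is to be worked out from the litres of oxygen given, and no conversion is stated. The definition has no item based on SpO2 alone.

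The next definition in section 6.4, clinical pulmonary oedema, accepts as respiratory distress a raised respiratory rate "and/or SpO2 <92% on room air", and requires this "with bilateral fine crepitations on chest auscultation".

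Section 4 lists the secondary outcome as "Proportion of patients with acute respiratory failure (see definition"), to be described for severe pre-eclampsia and for eclampsia. The SpO2/FiO2 ratio is also a secondary outcome in its own right, as is the use of oxygen, CPAP and mechanical ventilation.

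The data needed are collected. Section 7.4.2 records "Vital signs including GCS, pulse rate, blood pressure, respiratory rate, SpO₂, FiO₂, aural temperature" and other measurements at baseline. Section 5 says "Clinical examination will focus on signs of respiratory, neurologic and cardiac failure" and "The same clinical, LUS and echocardiographic assessment will be repeated between 24 h to 72 h" after delivery.

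**The concern.** A ratio with FiO2 in the denominator is high whenever FiO2 is low. On room air it stays above 315 until saturation is very low, so an oxygenation item built only on this cut may miss hypoxaemia in a woman who is not receiving oxygen. She is then counted only if her respiratory rate or visible effort qualifies her. This sits badly with section 3.1, which justifies the study partly by the limits of bedside examination and presents pulse oximetry as a way to quantify an oxygenation deficit.

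At the other end, once enough oxygen is running, the same cut is met whatever the saturation. The reported frequency of acute respiratory failure would then depend partly on who was given oxygen and how much, and a reader could not separate that from lung function.

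**Working it through.** **Inputs.** The cut of 315, the RR item and the signs item come from section 6.4, as does the room-air figure of 92%. The documents give no FiO2 value for room air or for any oxygen flow. All FiO2 values below, including 0.21 for room air, are therefore assumptions, shown as a range. The cut of 315 is a chosen threshold, so there is no derived figure in the plan to reproduce.

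**Formula.** The item is met when SpO2 (%) / FiO2 <= 315, that is, when SpO2 <= 315 x FiO2.

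| FiO2 (assumed) | 315 x FiO2 | Highest whole SpO2 that meets the item | SpO2 values below 92% that do not meet it |
|---|---|---|---|
| 0.21 | 66.15 | 66% | 67-91% |
| 0.24 | 75.6 | 75% | 76-91% |
| 0.27 | 85.05 | 85% | 86-91% |
| 0.28 | 88.2 | 88% | 89-91% |
| 0.29 | 91.35 | 91% | none |
| 0.30 | 94.5 | 94% | none |
| 0.32 | 100.8 | 100% (all women) | none |

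**Check at the edges.** 67/0.21 = 319 (not met) and 66/0.21 = 314 (met). 76/0.24 = 317 (not met) and 75/0.24 = 312.5 (met). 89/0.28 = 318 (not met) and 88/0.28 = 314 (met).

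**Where the behaviour changes.** A saturation of 91% meets the item from FiO2 91/315 = 0.289. A saturation of 100% meets it from 100/315 = 0.3175; for example, 100/0.32 = 312.5. The missed band therefore narrows quickly and has gone by about 0.29. By about 0.32 the item is automatic.

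**Worked case (hypothetical).** Room air, SpO2 85%, RR 24, bilateral crepitations, no signs of difficult breathing. The ratio is 85/0.21 = 405, above 315; RR is below 30; no signs are present. She does not have acute respiratory failure as defined. Her SpO2 is below 92% on room air and she has crepitations, so she does have clinical pulmonary oedema as defined.

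**The case against.** The strongest reply has four parts.

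- **The other items catch most of these women.** RR of 30 or more, or any sign of difficult breathing, qualifies a woman on its own, and the list of signs is open-ended. This stands as a limit on scope: the gap concerns only women with neither. It does not explain why an oxygenation item should add almost nothing on room air.
- **Hypoxaemia is reported elsewhere.** The ratio is a separate outcome, and the woman in the worked case appears under clinical pulmonary oedema. True, but a median and interquartile range of the ratio does not show who was hypoxaemic and left out of the proportion.
- **315 is a deliberate choice that matches the oxygenation row of Table 1.** This is fair, and Table 1 needs no change. There, however, the cut is one of several criteria required together; here it is the only oxygenation test.
- **The endpoint is one descriptive secondary proportion in an exploratory study.** This stands and limits how much weight the point can carry.

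A reader might also infer more than the documents support.

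- *The two definitions in section 6.4 contradict each other.* They do not: they define different constructs, and the 92% figure belongs to one that also requires crepitations.
- *The item is blind on low-flow oxygen in general.* It is not: at an assumed FiO2 of 0.28 only 89-91% is missed, and at 0.29 nothing below 92% is.
- *Acute respiratory failure will be under-reported overall.* This cannot be shown, because automatic positives from about 0.32 push the other way.
- *92% can be applied at any FiO2 as the protocol's own figure.* The protocol states it for room air only; wider use would be a new criterion.

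**Conclusion.** The concern holds in a limited form. The ratio item is almost inert on room air (66% or lower) and at FiO2 of about 0.24 (75% or lower), and is met at any saturation from about 0.32. It therefore largely tracks oxygen administration. Women on room air with SpO2 of 67-91%, RR below 30 and no signs of difficult breathing are not counted, although section 6.4 itself treats that saturation as respiratory distress in a neighbouring definition.

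The documents give no distribution of SpO2 or oxygen use, so neither the number of women affected nor the net direction of error can be computed. The room-air result rests on FiO2 0.21. Results on oxygen rest on FiO2 values that the plan does not link to litres.

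The primary lung ultrasound endpoints do not use this definition. Section 10 does not name acute respiratory failure among its regression outcomes, though that list is open. Section 4 gives no time point for the endpoint; if it is also derived from the repeated assessment after delivery, the same gap applies there. This is a worthwhile, inexpensive improvement to a secondary endpoint, not a flaw in the main result.

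**What to change.** These changes concern outcome classification only, not care.

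**Section 6.4.** Count the oxygenation item as met if SpO2/FiO2 is at or below 315, or if SpO2 is below 92% on room air, which is the protocol's own figure under its own condition. State one litres-to-FiO2 conversion and apply it to all patients. Leave the ARDS criterion in Table 1 unchanged.

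**Section 10.** Report:

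1. the proportion with acute respiratory failure under the definition as it now stands and under the extended one; the difference measures the room-air gap directly;
2. a breakdown by qualifying component: RR, ratio, room-air SpO2 below 92%, signs of difficult breathing;
3. the number who qualify by the ratio alone with SpO2 of 92% or more, which shows the dependence on oxygen delivery;
4. the number on oxygen with SpO2 below 92% and a ratio above 315 who are not otherwise counted.

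**Cost.** One clause, one stated conversion and a few descriptive rows. SpO2, FiO2 and RR are already recorded, and respiratory signs are already examined. The extended proportion is less comparable with studies that use the ratio alone and departs from the oxygenation criterion in Table 1; reporting both proportions covers this.

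**What remains.** A saturation of 90% would meet the oxygenation item on room air but not at FiO2 0.24 (90/0.24 = 375) or 0.28 (90/0.28 = 321); row 4 makes such women visible. The automatic positives from about 0.32 stay in both proportions; row 3 shows those who qualify in no other way.

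### Table 2 does not place every vital-sign value in exactly one MEWS band, so the score is undefined or ambiguous for some readings

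*Combined protocol and SAP*

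**What the plan says.** Section 6.4 (Case definitions) introduces the score with this sentence: "The modified early warning score ranges from 0 to 14 and is calculated as detailed in" Table 2. The table has seven parameters and three columns. The first is headed "Normal values (0 points"), the yellow alert carries 1 point and the red alert 2.

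The rows that matter here are:

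- **Systolic pressure:** 0 points at 100-139 mmHg, 1 point at "150- 180 or 90- 100" mmHg, 2 points at ">180 or < 90 mmHg".
- **SpO2:** 0 points at 96-100%, an empty yellow cell, 2 points below 95%.
- **Diastolic pressure:** 0 points at 50-89 mmHg, 1 point at 90-100, 2 points above 100. There is no low band.
- **Temperature:** 0 points at 36.0-37.4 °C, 1 point at "35- 36 or 37.5- 38°C", 2 points below 35 or above 38.
- **Heart rate:** 0 points at "50- 99 beats per" minute, 1 point at "100- 120 or 40- 50", 2 points above 120 or below 40.

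No other section says how to score a value that the table omits or lists twice. Section 6.2 enrols "All patients with severe pre-eclampsia or eclampsia admitted to hospital PCMH during the study period", and section 5 repeats the clinical assessment 24 to 72 h after delivery.

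**The concern.** A score that is calculated from a table needs every possible reading to land in exactly one band. Several readings in Table 2 land in none or in two. One of the gaps is ten units wide and lies in a part of the systolic range that is plausible for women with hypertensive disease, both at admission and at the repeat assessment.

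If the rule is applied literally, a woman with a value in a gap has no total, and whether she has one depends on her blood pressure. If staff fill the gap by judgement, two assessors can give different totals for the same vital signs. Either would weaken MEWS wherever it is reported or used.

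**Working it through.** **Step 1. Reproduce the stated range.** Seven parameters with a maximum of 2 points each give 7 × 2 = 14, and the minimum is 0. The stated 0 to 14 is correct. The fault lies in the bands, not in the total.

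**Step 2. Check coverage.** Each value was run through the bands of its row, in whole units (0.1 °C for temperature), counting how many bands contain it. Zero is a gap; more than one is an overlap.

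| Parameter | In no band | In two bands (0 and 1 point) |
|---|---|---|
| Respiratory rate | none | none |
| SpO2 | 95% | none |
| Temperature | none | 36.0 °C |
| Systolic pressure | 140-149 mmHg (10 integers) | 100 mmHg |
| Diastolic pressure | below 50 mmHg | none |
| Heart rate | none | 50 |

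A small addition: section 7.4.2 records temperature as the average of both ears. Readings of 37.4 and 37.5 average to 37.45 °C, which falls between the 0-point and 1-point bands unless a rounding rule is set.

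**Step 3. Points at stake.**

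- Systolic 140-149 lies between the 0-point and 1-point bands, so allotting it to either neighbour moves the total by at most 1.
- Each overlap is a choice between 0 and 1, so again 1 point.
- SpO2 95% lies between a 0-point and a 2-point band, so the difference could be 2.
- Diastolic pressure below 50 has a 0-point neighbour on one side only. Its points depend on whether the source has a low band.

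**Step 4. How often the systolic gap could arise.** The documents give no blood pressure distribution, so this step is illustrative. Assume systolic pressure is normal with mean m and SD s, recorded in whole mmHg:

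P(gap) = Φ((149.5 − m)/s) − Φ((139.5 − m)/s)

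For m = 150 and s = 20 this is Φ(−0.025) − Φ(−0.525) = 0.190.

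| Assumed mean (mmHg) | SD 15 | SD 20 | SD 25 |
|---|---|---|---|
| 140 | 0.250 | 0.193 | 0.156 |
| 150 | 0.245 | 0.190 | 0.155 |
| 160 | 0.156 | 0.147 | 0.131 |
| 170 | 0.065 | 0.089 | 0.095 |
| 180 | 0.018 | 0.042 | 0.059 |

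The range is about 2% to 25% of readings. Under the same assumptions the overlap at systolic 100 holds at most 0.44% of readings (mean 140, SD 25). The frequencies of SpO2 95% and diastolic pressure below 50 cannot be derived from the documents.

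**Step 5. Where the score is used.** MEWS is absent from the synopsis, the objectives and outcomes in section 4, the baseline assessments in section 7.4 and the statistics in section 10. Section 10 names several outcomes for its logistic models but lists no candidate covariates.

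**The case against.** The strongest reply is that nothing in the plan depends on this score. MEWS is defined and then not mentioned again, so no planned result changes. That stands, and it limits the importance of the point.

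Three stronger readings are tempting, and the documents do not support them.

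- **The score cannot be calculated for many women.** This needs a blood pressure distribution, which the documents do not give. The share ranges from about 2% to 25% on assumptions alone.
- **Severity would be understated if the gap were scored 0.** This holds only if the source gives points at 140-149 mmHg. If the source's normal band extends to 149, then 0 is right. Neither bias nor its direction can be asserted.
- **The section 10 models would be compromised.** MEWS could be entered as a covariate, but the plan does not say so.

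It can also be said that the table was read from a PDF and its rows are broken across lines. A lost cell or symbol is a real possibility for SpO2, where the middle cell is empty. It is a poor explanation for the systolic row, where both yellow ranges are legible, or for the three overlaps, which consist of numbers that are present.

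Finally, staff may in practice work from the cited chart. The protocol, however, names Table 2 as the basis of the calculation.

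**Conclusion.** The point holds as a defect in a definition. As written, Table 2 leaves MEWS undefined for systolic 140-149 mmHg, SpO2 of exactly 95% and diastolic pressure below 50 mmHg. It leaves the score ambiguous by 1 point at systolic 100 mmHg, temperature 36.0 °C and heart rate 50.

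The systolic gap is the one most likely to be met, and it puts at most 1 of 14 points at stake per assessment. Its 2-25% frequency rests entirely on assumed normal distributions with mean 140-180 mmHg and SD 15-25. The single-value overlaps should affect few women.

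No primary or secondary endpoint is touched. The consequence is confined to MEWS itself, wherever it is reported or used, and the importance is low.

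**What to change.** Reconcile Table 2 with its source so that every possible value of each parameter falls in exactly one band. The protocol cites two references for the score (34 and 35), so it should also state which one governs the bands. The investigators should take the cut-points from that source; this review does not propose any. Add a rounding rule for averaged temperature.

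Then calculate MEWS from the recorded vital signs with the corrected bands, and recompute any total already entered by hand. Section 7.4.2 already records blood pressure, SpO2, temperature and pulse in the CRF, so the five affected rows can be rescored without new data collection. The cost is a corrected table and one scoring rule, with no burden on patients.
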